7.1 Study closure

The study will be closed after one year (9 months pregnancy + 3 months after giving birth) the last 12 months appointment of the last recruited patient is completed, and all data have been received.

7.2 Study outcome measures

	Intervention/procedure	Outcome measures
Primary outcome	DUS	
 • Patency • Blood flow direction(antegrade/retrograde) • Peak reflux velocity
Secondary outcomes	VFI	
 • Patency • Blood flow direction(antegrade/retrograde) • Peak reflux velocity
	Truncated cone tool	
 • C1 • C2 • h
	PPG	Severity of venous reflux by measuring Venous refiling time (VRT) (Abnormal less than 20 sec)
	Genomic blood test	Genomic DNA
	Hormonal Blood test	Estroil (E3) levels, progesterone serum levels
	AVVQ questionnaire	Outcome of quality of life (0-100). 0 least severe (good quality of life), 100 most severe (low quality of life).

8 Statistics and data analysis

8.1 Sample size

An exact binomial test with a nominal 5% two-sided significance level will have 91.27% power to detect the difference between the null hypothesis proportion, π_0 of 0.25 and the Alternative proportion, π_1 , of 0.1 when the sample size is **70**.

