1.2 Rationale for current study

Regardless of the underlying pathophysiological cause, VV may have a negative social impact on patient's life and negative economic impact on health care budget. VV if left untreated can progress to late stages of chronic venous insufficiency (CVI) which include skin changes and ulceration (Adhikari *et al.*, 2000). Ulcers lower patient's quality of life and may result in social isolation, depression, reduce the ability to work and patients will be dependent on others (Evans *et al.*, 1994; Cesarone *et al.*, 2002). Furthermore, venous disease is costly to manage for healthcare service. For example, the cost of managing chronic wounds caused by ulcers in the UK National Health Service (NHS) during 2005 to 2006 was estimated from 2.3 to 3.1 billion pounds which was equivalent to 3% of total UK health care budget (Posnett, J. and Franks, 2007). Interestingly, the cost was increased between 2012 to 2013 when cost was estimated at 5.3 billions of pounds annually which consume 4% of the total health UK health care budget (Guest *et al.*, 2015).

1.3 Research hypothesis:

The development of post-partum chronic venous insufficiency is predictable and caused by both mechanical and hormonal factors.

2 Study aim and objectives:

The primary aim of this proposed study is to better understand the pathophysiology of VV in pregnant women. This aim will be achieved by meeting the following objectives:

Primary objective:

To develop an antenatal test to predict the risk of developing VV post-partum.

Secondary aims:

1. To evaluate mechanical factors causing VV in pregnancy
2. To evaluate hormonal factors causing VV in pregnancy.
3. To determine whether lower limb pain during pregnancy is related to changes in lower limb venous system.

3 Methods

3.1 Study design:

A prospective longitudinal study will be undertaken to assess the development of VV among pregnant women. This study will follow up patients for one year, starting by following up pregnant women from the first trimester of pregnancy to the end of the second and third trimester. Last follow up will be performed three months after giving birth. Consequently, this proposed prospective study will be conducting four follow ups for each participant.

3.2 Recruiting pregnant women in their first trimester:

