3.3.2 Protocol for Duplex ultrasound scan (DUS)

All recruited pregnant women be scanned by duplex ultrasound scan (DUS) to investigate the evidence of VV. The examination will be bi lateral for each patient. The patient will be asked to remove their clothes to expose the lower limb from groin to ankle. Patient will be examined standing to evaluate valves competency against gravity. This is because veins are more dilated while standing which make it easier and more accurate to assess. This examination is considered intimate; therefore, a chaperone will be offered. The scan duration will take 30-45 min and patients may sometimes feel dizzy during the examination. To overcome this issue, patients will be asked to sit and take a rest during the examination.

There are two main techniques which will be applied to all venous segments. Firstly, B mode technique. B mode technique will be used to evaluate vein patency in transverse scan plane by observing the compressibility of veins to rule out any possibility of blood clots. Secondly, Spectral (Pulse wave) doppler technique will be used to evaluate venous flow characteristics (phasicity, spontaneity and direction flow) in longitudinal scan plane by applying manual distal augmentation to assess the reflux duration. All scans and measurements will be performed on SuperSonic Imagine's Aixplorer ® ultrasound system. Following this, 9 MHz linear ultrasound probe will be placed on the patient skin over the venous blood vessel to be scanned, with the use of coupling gel between the skin and the probe.

The scan will start by evaluating the deep and superficial veins system. Firstly, deep veins will be assessed by scanning the Common femoral vein (CFV) at the groin for patency and flow. Any abnormality in CFV indicates iliac vein obstruction therefore iliac veins and inferior vena cava should be examined. The examination will be continued by scanning the length of femoral vein (FV) (proximal to distal), popliteal vein and calf veins. Any thrombus or incompetence (Incompetent veins are defined as a reflux time more than 0.5 seconds) will be recorded.

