8.2 Analysis plan

All analyses will be performed based on the intention of follow-up. The analysis population will include all participants enrolled in the study, including those who developed varicose veins during pregnancy and those who do not.

Analysis of primary and secondary outcomes:

Venous patency and Peak reflux time recordings from VFI scan will be correlated with Venous patency and peak reflux time recordings from DUS scan. This will be performed using descriptive summary statistics. Mixed multivariable logistic regression will be used to model venous patency and peak reflux velocity in each scan.

Secondary outcome which include measuring the circumferences (C1, C2) and length of segments (h) using Truncated cone method. Calculated volume will be determined by summing segment volumes derived from the truncated cone formula. Pearson product moment correlations, paired t tests, and linear regression tests will be used to assess relative association and absolute differences between calculated volumes in each follow up.

Secondary outcome which include PPG will be analysed by comparing the mean value for the venous refilling time (VRT) by Student's *t* test, agreement between DUS and PPG classification was expressed as a kappa (**K**) value.

Genomic DNA blood samples results will be correlated with the UK biobank study. Test statistics will be used to identify genetic variants that influence varicose vein susceptibility.

Each hormonal blood samples results including Estroil (E3) and progesterone serum levels will be correlated with the results of the next follow up to provide comprehensive information about increased hormonal levels in pregnancy and varicose veins development.

Outcome of quality of life statistical analysis will be performed using the Statistical Package for the Social Sciences (SPSS 23.0) for Windows. Evaluation of AVVQ consisted of quality of life in first trimester, second trimester, third trimester and three months after giving birth will be done using the Friedman test.

8.3 Data analysis:

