The data obtained will be subjected to statistical analysis by an independent biostatistician. SPSS Version 23.0 or/ and STATA Version 10.0 will be used for statistical analysis. Measures such as the mean and standard deviation or median and interquartile range will be used to summarise continuous variables such as age and BMI. Tables reporting the numbers and percentages will be used for categorical variables such as varicose veins and smoking. Chi square or Fisher's exact test will be used to compare categorical variables such as varicose veins and smoking at the final trimester. The t-test or Mann-Whitney test will be used to compare continuous variables such as age with varicose veins at the final trimester. The paired t-test or Wilcoxon signed-rank test will be used to compare BMI between first and third trimester. The Kappa statistic will be used to compare DUS and VFI regarding direction and velocity. Longitudinal analysis will be used to look at factors associated with varicose veins. Factors include age, BMI, smoking, ethnicity, pregnancies and family history. A significance value (p-value) less than 0.05 is considered statistically significant.

9 Regulatory issues

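### Section 8.1's 91.27% power belongs to a one-sample test that sections 8.2 and 8.3 do not plan, for an event and visit that 8.1 does not name

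*Combined protocol and SAP*

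**What the plan says.** **Sample size (8.1).** The section is a single sentence. "An exact binomial test with a nominal 5% two-sided significance level will have 91.27% power" for a null proportion of 0.25 against an alternative of 0.10 with 70 participants. It does not say what is being counted or at which of the four visits, and it gives no source for either proportion.

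**Objective and outcome.** The primary objective in section 2 is "To develop an antenatal test to predict the risk of developing VV post-partum". The primary outcome in 7.2 is a set of three duplex ultrasound (DUS) measures: patency, flow direction and peak reflux velocity. No single binary event or time point is chosen from them.

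**Planned analyses (8.2 and 8.3).** For the scan outcomes, 8.2 says "Mixed multivariable logistic regression will be used to model venous patency and peak reflux velocity in each scan". For VV as a category, 8.3 says "Tables reporting the numbers and percentages will be used for categorical variables such as varicose veins and smoking", and it uses chi-square or Fisher's exact test to "compare categorical variables such as varicose veins and smoking at the final trimester".

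**Who is analysed.** Section 8.2 says "The analysis population will include all participants enrolled in the study". Section 4.3 excludes women who miss scans after the first visit and incomplete cases such as intrauterine death. Section 6 withdraws women with an incidental finding such as DVT. No allowance for loss is stated.

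**The concern.** A power statement means something only for a named test of a named quantity. Here the test is named in 8.1 but appears nowhere in the analysis plan, and the quantity is not named at all. The sentence is the only justification given for 70 women, so a reader may well take it as the study's ability to answer its main question. Nothing in the documents makes that link.

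Even if 0.25 and 0.10 were VV prevalences, showing that prevalence differs from 25% would not show that an antenatal measurement predicts who develops VV after delivery. What 70 women can deliver for that objective (number of events, width of intervals, number of factors that can be modelled) is not stated.

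**Working it through.** **1. Reproduce the plan's figure.** Inputs from 8.1: p0 = 0.25, p1 = 0.10, n = 70, exact binomial, two-sided 5%. Taking 0.025 per tail, the rejection region is the largest c with P(X ≤ c | p0) ≤ 0.025 together with the smallest d with P(X ≥ d | p0) ≤ 0.025.

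- Lower tail: P(X ≤ 10 | 70, 0.25) = 0.0220, and P(X ≤ 11) = 0.0439, so c = 10.
- Upper tail: P(X ≥ 26 | 70, 0.25) = 0.0163, so d = 26.
- Attained size: 0.0220 + 0.0163 = 0.0383.
- Power: P(X ≤ 10 | 70, 0.10) + P(X ≥ 26 | 70, 0.10) = 0.9127, the second term being negligible.

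This is 91.27%, as stated. The match identifies what was powered: one proportion compared with a fixed 0.25. A one-sided 5% test would give 95.6%, and swapping the two proportions would give 92.0%.

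**2. Look for that test in the plan.** Sections 8.2 and 8.3 list:

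- descriptive comparison of DUS with vector flow imaging (VFI), and mixed logistic regression;
- Pearson correlation, linear regression, and paired and Student's t tests;
- kappa and the Friedman test;
- unspecified test statistics for genetic variants;
- chi-square or Fisher's exact, Mann-Whitney and Wilcoxon tests;
- a longitudinal analysis of factors associated with VV.

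None compares a proportion with 0.25. Fisher's exact test is used here to compare categorical variables with each other, so it does not supply the missing one-sample test. A VV percentage will be tabulated, but tabulating is not testing.

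**3. Look for the event and visit.** Section 8.1 gives neither. Section 7.2 offers three measures, section 3.1 has four visits, the VV comparisons named in 8.3 are at the final trimester, and the primary objective is post-partum. The reader cannot tell which of these 0.25 and 0.10 describe.

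**4. Dependence on all 70 women.** The same calculation with fewer evaluable women follows. Every loss is an assumption, since the documents give no rate.

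| Evaluable women | Assumed loss | Reject at | Power |
|---|---|---|---|
| 70 | none | ≤10 or ≥26 | 91.3% |
| 69 | one woman | ≤9 or ≥26 | 85.2% |
| 66 | about 5% | ≤9 or ≥25 | 88.0% |
| 63 | 10% | ≤8 or ≥24 | 82.5% |
| 56 | 20% | ≤7 or ≥22 | 80.7% |

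At n = 69, P(X ≤ 10 | 0.25) = 0.0255, just over 0.025, so the lower cut-off drops to 9. For n from 52 to 69 the highest power is 88.9% (n = 65), so none reaches 90%.

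**5. What 70 women could give for the primary objective.** This is an illustration only. It assumes that the event is VV per woman, that its rate lies between 10% and 25%, and that all 70 are assessed.

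- Expected events: 70 × 0.10 = 7 to 70 × 0.25 = 17.5.
- 95% Clopper-Pearson intervals: 4.1% to 19.5% at 7/70, and 16.0% to 37.6% at 18/70.
- Section 8.3 lists six factors (age, BMI, smoking, ethnicity, pregnancies, family history): 7/6 = 1.2 to 17.5/6 = 2.9 events per factor, before hormones, limb volume or refilling time are added.

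**The case against.** The strongest reply has four parts.

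**The study is observational and the arithmetic is right.** Section 8.1 never says that 91.27% is the power for the primary objective. That is true, and the point here is not a miscalculation. But the figure is the sole justification for the sample size, and it corresponds to nothing that will be analysed. That part stands.

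**The unit is known.** Because "The examination will be bi lateral for each patient", a reader might infer that 0.25 and 0.10 could be per limb, giving 140 paired limbs and breaking the binomial assumption. The documents do not support this. The study summary gives a population of 70 pregnant women and 8.1 uses n = 70, so the woman is the counting unit. What remains is narrower: whether one affected leg makes a woman an event.

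**The attrition effect is modest.** The fall from 91.3% to 85.2% on losing one woman is largely discreteness in the exact test: power is higher again at 65 or 66 women than at 69. All losses are assumed. This is accepted, and attrition is the secondary point.

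**Section 9.2 keeps women in the analysis.** A reader might infer a further contradiction from its statement that participants remain in for follow-up and analysis. That sentence covers only women whose clinician gives alternative treatment. It does not address women who miss scans or are withdrawn for an incidental finding, so it is not relied on here.

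**Conclusion.** The concern holds. The 91.27% is correctly computed for a two-sided exact one-sample test of 0.25 against 0.10 in 70 women. No such test is planned, and the event and visit are unnamed. This conclusion comes from reading 8.1 against 8.2, 8.3, section 2 and 7.2, and needs no assumed rate.

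The secondary point also holds, at modest size. The stated power needs all 70 women evaluable, and at the assumed losses tabulated, of one woman up to 20%, it would be about 81% to 88%. The plan both removes women after entry and says that everyone enrolled is analysed, without saying how the two fit together.

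A reader might go further and infer that 70 women are too few. The documents do not establish that. They give no post-partum VV rate and no target precision for the predictive test. The event counts and intervals above rest on treating 10% to 25% as a VV rate per woman, which 8.1 does not say.

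The sample size rationale should be corrected; data collection is unaffected.

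**What to change.** Keep 70 women and take one of two routes.

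**(a) Drop the power claim.** Remove 91.27% as the justification and describe 70 as a fixed sample size. State what it gives for the primary objective, with assumptions labelled. For example: if VV per woman is 10% to 25% and all 70 are assessed, expect about 7 to 17.5 events, with 95% exact intervals of about 4% to 20% at 7/70 and 16% to 38% at 18/70, and about 1 to 3 events per factor for the six factors in 8.3.

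**(b) Keep a power claim, if a comparison with 0.25 serves a stated objective.** In 8.1, name the event per woman (including whether one affected leg counts) and the visit. Add that one-sample exact test to 8.2. Restate the power at the expected number of evaluable women, with the assumed loss given.

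Under either route, reconcile the all-enrolled analysis population in 8.2 with the removals in 4.3 and section 6.

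**Cost.** Wording only: no extra women, visits or procedures. Under (a) the power figure disappears. Under (b) it becomes less favourable once any of the losses considered here is assumed.

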8.2 Analysis plan

All analyses will be performed based on the intention of follow-up. The analysis population will include all participants enrolled in the study, including those who developed varicose veins during pregnancy and those who do not.

Analysis of primary and secondary outcomes:

Venous patency and Peak reflux time recordings from VFI scan will be correlated with Venous patency and peak reflux time recordings from DUS scan. This will be performed using descriptive summary statistics. Mixed multivariable logistic regression will be used to model venous patency and peak reflux velocity in each scan.

Secondary outcome which include measuring the circumferences (C1, C2) and length of segments (h) using Truncated cone method. Calculated volume will be determined by summing segment volumes derived from the truncated cone formula. Pearson product moment correlations, paired t tests, and linear regression tests will be used to assess relative association and absolute differences between calculated volumes in each follow up.

Secondary outcome which include PPG will be analysed by comparing the mean value for the venous refilling time (VRT) by Student's *t* test, agreement between DUS and PPG classification was expressed as a kappa (**K**) value.

Genomic DNA blood samples results will be correlated with the UK biobank study. Test statistics will be used to identify genetic variants that influence varicose vein susceptibility.

Each hormonal blood samples results including Estroil (E3) and progesterone serum levels will be correlated with the results of the next follow up to provide comprehensive information about increased hormonal levels in pregnancy and varicose veins development.

Outcome of quality of life statistical analysis will be performed using the Statistical Package for the Social Sciences (SPSS 23.0) for Windows. Evaluation of AVVQ consisted of quality of life in first trimester, second trimester, third trimester and three months after giving birth will be done using the Friedman test.

8.3 Data analysis:

The data obtained will be subjected to statistical analysis by an independent biostatistician. SPSS Version 23.0 or/ and STATA Version 10.0 will be used for statistical analysis. Measures such as the mean and standard deviation or median and interquartile range will be used to summarise continuous variables such as age and BMI. Tables reporting the numbers and percentages will be used for categorical variables such as varicose veins and smoking. Chi square or Fisher's exact test will be used to compare categorical variables such as varicose veins and smoking at the final trimester. The t-test or Mann-Whitney test will be used to compare continuous variables such as age with varicose veins at the final trimester. The paired t-test or Wilcoxon signed-rank test will be used to compare BMI between first and third trimester. The Kappa statistic will be used to compare DUS and VFI regarding direction and velocity. Longitudinal analysis will be used to look at factors associated with varicose veins. Factors include age, BMI, smoking, ethnicity, pregnancies and family history. A significance value (p-value) less than 0.05 is considered statistically significant.

9 Regulatory issues

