Next, the patient will be asked to stand on a step facing the sonographer to assess the incidence of varicose veins using Duplex ultrasound (DUS) and vector flow imaging (VFI). While patient is standing, Truncated cone tool will be performed immediately by measuring leg circumferences in each segments of each limb to produce accurate measurements of lower limbs volume. Following this, patient will be asked to sit on a chair for perform Iliac vein compression test (venous outflow function) using photoplethysmography (PPG) technique. Finally, patient's quality of life assessment will be evaluated by using Aberdeen Varicose Veins Questionnaire (AVVQ) check list (Klem, Sybrandy and Wittens, 2009). Thereafter, the patient will be thanked for their participation and excused.

Clinical Laboratory tests will be managed and performed by experienced research professionals in the area of vascular surgery. Four appointments will be arranged for each patient to investigate DNA genomic testing and Estriol (E3) and progesterone hormonal testing. First appointment during first trimester will include both genomic DNA and hormonal blood tests. The three remaining appointments in the second trimester, third trimester and three months after giving birth will include hormonal blood samples only. Patients will be entitled to exit the study at any time without providing a reason, this is clearly stated on our information sheet and consent form. Verbal consent will be requested before all follow-up ultrasound scans.

Researchers will ensure that demographic data, ultrasound data, lower limb volume and iliac vein compression measurements, histopathological results and quality of life

assessment results will be collected and stored in such a way that confidentiality is preserved. All data will be pseudonymised by replacing names with research codes and by keeping any identifying information separate from the main dataset.

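### The final-trimester tests in 8.3 measure prevalent varicose veins, not their development, and no planned analysis names an at-risk set or a first-scan term

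*Combined protocol and SAP*

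**What the plan says.** **The question is onset.** Section 3.1 states: "A prospective longitudinal study will be undertaken to assess the development of VV among pregnant women". The primary objective in section 2 is "To develop an antenatal test to predict the risk of developing VV post-partum".

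**Entry does not require unaffected veins.** The only pre-registration check (4.1) is a blood test confirming pregnancy. Inclusion (4.2) rests on age, consent and willingness to be followed. The vein-related exclusions (4.3) are congenital vascular abnormality, signs of acute deep vein thrombosis and severe injury of the great saphenous vein. Existing VV and superficial reflux are not listed.

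**The analysis uses everyone.** Section 8.2: "The analysis population will include all participants enrolled in the study, including those who developed varicose veins during pregnancy and those who do not". In 8.3, chi-square or Fisher's test will "compare categorical variables such as varicose veins and smoking at the final trimester", and the t-test or Mann-Whitney test will "compare continuous variables such as age with varicose veins at the final trimester". A further sentence reads: "Longitudinal analysis will be used to look at factors associated with varicose veins. Factors include age, BMI, smoking, ethnicity, pregnancies and family history". Hormone results are to be correlated with those of the following visit "to provide comprehensive information about increased hormonal levels in pregnancy and varicose veins development".

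**The first scan is available.** Bilateral duplex ultrasound (DUS) is done in the first trimester and at three later visits (3.3.2, 3.4, 7).

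**The concern.** VV status at the final trimester is a prevalence measure. It adds disease already visible at the first scan to disease that appeared afterwards, and the 8.3 tests have no means of separating the two. This can mislead in two ways:

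- A factor that truly raises new onset looks weaker when entry disease is equally common in both comparison groups.
- A factor with no effect on onset looks harmful if it goes with entry disease. Previous pregnancies and family history, both on the 8.3 list, might do so, although the documents do not show it.

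The phrase in 8.2 about women who developed VV during pregnancy hints at a new-onset contrast but does not define one. A woman affected at her first scan has no clear place in it.

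The plan also never says which DUS finding counts as VV. Section 1.1 describes tortuous, dilated superficial veins, while the threshold of more than 0.5 seconds in 3.3.2 defines an incompetent vein. Without a fixed outcome, neither being free of VV at the first scan nor being a new case can be determined.

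**Working it through.** **1. The plan's own figure.** Section 8.1 gives 91.27% power for a two-sided 5% exact binomial test of 0.25 against 0.10 with 70 women. With at most 2.5% in each tail, the test rejects at X ≤ 10 or X ≥ 26. Its exact size is 0.0383 and its power 0.9127. The figure reproduces, so this point does not rest on an arithmetic error.

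**2. Assumed inputs.** The documents give none of these: q, the proportion affected at the first scan (5, 10, 20%); r, the risk of new onset by the final trimester among women free at the first scan; and p, the share of entry disease that persists (1 or 0.5).

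**3. Formulas.**
- Final-trimester prevalence: F = qp + (1 − q)r.
- Share of it already present at the first scan: qp/F.
- Observed risk ratio, onset risks r1 and r0, equal q in both groups: [qp + (1 − q)r1] / [qp + (1 − q)r0].

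**4. Results.** Shares use r = 10%. Risk ratios use r1 = 15% and r0 = 5%, a true ratio of 3.

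| q | Share, p = 1 | Share, p = 0.5 | Ratio, p = 1 | Ratio, p = 0.5 |
|---|---|---|---|---|
| 5% | 0.05/0.145 = 34% | 0.025/0.12 = 21% | 0.1925/0.0975 = 1.97 | 0.1675/0.0725 = 2.31 |
| 10% | 0.10/0.19 = 53% | 0.05/0.14 = 36% | 0.235/0.145 = 1.62 | 0.185/0.095 = 1.95 |
| 20% | 0.20/0.28 = 71% | 0.10/0.18 = 56% | 0.32/0.24 = 1.33 | 0.22/0.14 = 1.57 |

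With r = 25% the shares are 17/31/50% (p = 1) and 10/18/33% (p = 0.5).

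**5. A factor with no effect on onset** (r = 10% in both groups). If entry prevalence is 15% against 10%, the observed ratio is 0.235/0.19 = 1.24 (p = 1) or 0.16/0.14 = 1.14 (p = 0.5). At 20% against 5% it is 0.28/0.145 = 1.93 or 0.18/0.12 = 1.50.

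**6. Number at risk.** 70 × (1 − q) is 66.5, 63 and 56 women before losses, so at most about 66, 63 and 56. Expected events at 10% onset are 66.5 × 0.10 = 6.7, 6.3 and 5.6. At 25% onset they are 16.6, 15.8 and 14.0.

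**7. Power, only if the 8.1 proportion means incidence.** The same exact test gives 88.0% at 66 (lower rejection limit X ≤ 9), 82.5% at 63 (X ≤ 8) and 80.7% at 56 (X ≤ 7).

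**The case against.** The plan is vague as much as wrong. The mixed model and the longitudinal analysis both use repeated scans and could be built to study onset. The factor list is not said to be complete, so first-scan status might be added. This stands, and it is why the firm conclusion is confined to the final-trimester tests, the only VV tests whose form is stated.

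Those tests are simple comparisons given as examples, and the longitudinal sentence speaks of association. All-comer association is a legitimate question. This also stands: for the 8.3 tests the correction is largely a label. The label matters because the study's stated purpose is development. The word incidence in 3.2 adds little support, since it describes a scan that is also done at the first visit, where new onset cannot be measured.

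A reader might infer that the primary objective is undone by these tests. The documents do not support that. The objective concerns VV post-partum, and no 8.3 test is tied to the three-month scan. That objective suffers mainly from having no stated event or prediction analysis.

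A reader might also infer that the sample size is wrong. Section 8.1 does not name the event behind 0.25 and 0.10, so the lower powers apply only if incidence is meant.

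**Conclusion.** The concern holds for the final-trimester tests. Followed as written, they measure prevalence and cannot support statements about the development of VV. No other planned analysis is specified well enough to fill the gap. This follows from the text and needs no assumed figure.

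The size of the bias is unknown. The illustrated shares and risk ratios depend wholly on assumed entry prevalence, onset risk and persistence, and on which DUS finding is taken as VV. It would be too strong to say that a large bias has been shown, or that a listed factor will give a false signal in this cohort.

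It would also be wrong to read first-scan disease as disease that preceded pregnancy. Section 1.1 says VV may begin in the first trimester, and 4.4 places the first assessment at the end of it.

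The plan should be corrected before analysis. The data needed are already being collected, and a definition of new cases chosen after seeing the results would be open to influence from them.

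**What to change.** Amend 8.2 and 8.3, using the scans already planned:

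1. State one DUS-based outcome and apply it in the same way at all four scans. If it is superficial reflux of more than 0.5 seconds, name it as such and not as VV itself.
2. For any analysis of development, restrict to women free of that outcome at the first-trimester scan. When a predictor is measured at a later visit, require freedom from the outcome up to and including that visit. Otherwise second- or third-trimester hormones, venous refilling time or limb volume would again be related to disease already present. State whether the unit is the woman or the limb, with clustering by woman if the limb. For the primary objective, the event is that outcome at the three-month post-partum scan.
3. Keep all women in the all-comer analyses, label the 8.3 tests as prevalence at the final trimester, and describe early disease as present at first scan.
4. Report the numbers at risk, lost and with events.

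**Cost.** No extra visits or scans, but the outcome definition is a real addition to the protocol. At most about 66, 63 or 56 of 70 women are at risk at 5, 10 or 20% entry prevalence. Losses reduce this further: 4.3 excludes non-attenders and intrauterine deaths, and section 6 withdraws women with an incidental thrombosis. With so few events the prediction analysis will be largely descriptive. Onset before the first scan drops out of the incidence analysis, which bears on the hormonal aim and should be stated as a limitation. If the 8.1 proportion is meant as incidence, its power should be restated for the number at risk.
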